9.1 Agent Administration

Treatment will be administered on an outpatient basis. Reported adverse events and potential risks for ponatinib are described in Sections 2, 7, 9 and the Investigator's Brochure. No investigational or commercial agents or therapies other than those described below may be administered with the intent to treat the patient's malignancy.

9.2 Ponatinib

Ponatinib will be prescribed at a flat dose. The planned dose is 45mg QD for FGFR related cohorts and 30mg for RET related cohorts. Higher doses/schedules than 45mg QD will not be explored. However, FGFR related cohorts may be explored at 30mg if 45mg is not tolerated and there is insufficient data to determine efficacy, or if 45mg is tolerated and there is evidence (radiographic or pharmacodynamic) of efficacy, 30mg may be explored to establish a safer dose longterm. Tablet(s) should be taken by the patient at the same time each day with or without food. In patients who are not already on a statin or anticoagulation (aspirin, heparin, coumadin or equivalent), in the absence of contraindications prophylaxis with 81mg aspirin and 10mg atorvastatin (or equivalent) is recommended to start the day after commencement of dosing with the ponatinib.

9.3 Exploration of dosing other than 45mg QD

A once daily dose of 45mg of ponatinib taken orally has shown activity in patients with chronic myeloid leukemia and is taken to represent the recommended phase II dose of the drug. The geometric mean trough concentration at 45mg was 61.9nM and the mean steady state C_{max} was 149nM, suggesting that 45mg will achieve efficacious levels against FGFR1-4 in vivo (Gozgit et al, 2012). However, these assumptions must be proven in vivo in humans and the use of pharmacodynamic markers to confirm levels active against the FGFR will be employed in the initial 12 patients treated within the study at 45mg QD and additional doses/dose regimens explored as needed in the absence of either pharmacodynamic effects or clear clinical activity in relevant molecularly defined populations.

Fibroblast growth factor 23 (FGF23) is the most recently discovered FGF. Unlike other canonical FGFs, which exert their paracrine and autocrine effects by binding heparan sulfate in the extracellular matrix, topological differences in the heparin-binding region of FGF23 enable it to avoid capture in the extracellular matrix (Shimada et al, 2001). As a result, FGF23 functions as an endocrine hormone that regulates phosphorus homeostasis through binding to FGFR 1-4 and klotho, its coreceptor in the kidney

and parathyroid glands (Urakawa et al, 2006). The primary physiological actions of FGF23 are to augment phosphaturia by downregulating expression of sodium-phosphate cotransporters in the renal proximal tubule and to decrease circulating concentrations of 1,25-dihydroxyvitamin D by inhibiting renal expression of the 1,25-dihydroxyvitamin D-synthesizing CYP27B1 (1- α -hydroxylase) and stimulating expression of the catabolic CYP24 (24-hydroxylase) (Ben-Dov et al, 2007).

Plasma FGF23 measurement can be used as an indicator of FGF inhibition. In fact, Dovitinib, another multi-targeted tyrosine kinase, has been shown when used in patients with melanoma to produce a 68% mean increase in plasma FGF23 during treatment which peaked at 15 days of cycle 1 (Shi et al, 2009). Hence similar effects can be expected with the administration of Ponatinib and we will check FGF23 levels on Cycle 1 Days 1, 8 and 15, with increases in the order of 50% percent in plasma FGF23 measurements compared to Cycle 1 Day 1 considered indicative of FGFR inhibition. In addition, FGFR inhibition can be easily assessed by measurement of urinary excretion of phosphorus (normal: 10-15%). FGFR inhibition should be accompanied with a decrease in the fraction excretion of phosphorus and an elevation of serum phosphorus concomitantly when the elevated plasma FGF23 levels are detected. Consequently on the same days in Cycle 1 we will also assess intact PTH, Calcium, phosphorus and creatinine in serum and phosphorus and creatinine in urine.

In the absence of either pharmacodynamic effects or clear clinical activity in relevant molecularly defined populations within the first 12 patients treated at 45mg QD, because of the newly identified risk factors with ponatinib, higher doses/exposures will not be explored. The National Cancer Institute Common Terminology Criteria for Adverse Events (NCI-CTCAE, Version 4.0) will be used to grade adverse events. A dose level will be considered tolerable following completion of 1 cycle (28 days) in 9 of 12 patients in the absence of dose limiting toxicity (DLT). If ≥ 3 patients experience DLT at this dose level, the dose level will be deemed non-tolerated. A DLT will be defined by the adverse events listed below that are considered possibly, probably, or definitely related to ponatinib.

- Any non-hematological toxicity \geq grade 3 (excluding diarrhea, nausea, or vomiting in the absence of optimal anti-diarrheal or anti-emetic therapy).
- Grade 4 neutropenia lasting > 5 days or associated with fever > 100.5 °F.
- Grade 4 thrombocytopenia.
- Any treatment delay of > 14 days due to drug-related toxicity.

Patients must complete 24 of the planned 28 days (85%) dosing of ponatinib in Cycle 1 to be evaluable in the absence of DLTs. If not evaluable for the purposes of determination of drug tolerability, the patient may continue to be treated, but will be replaced if needed to determine adequate numbers for tolerability and dose decision making.

As the IC50 for RET is an order of magnitude lower than for FGFR1, RET cohorts will commence at 30mg and the logic relating to efficacious exposures for doses based on FGFR1 PD markers/responses will not automatically be applied to the *RET*+ cohort and if activity in *RET*+ cases is noted at the time this will not influence the decision-making re dose alteration in the *FGFR1*+ cohorts. However, if ≤ 2 responses are seen in the initial *RET*+ cohort but *FGFR1*+ responses or FGFR PD modulation have been noted at 45mg and 45mg appears to be acutely well tolerated per DLT criteria we will reconsider this logic and accrue an additional *RET*+ cohort at 45mg. If no evidence of FGFR pathway modulation or of clinical benefit has been seen in *FGFR*+ cases across all achievable alternative doses, accrual to

FGFR1+ cohorts will be suspended. If doses other than 45mg QD are explored, the number of patients in each biomarker selected cohort will be modified to include only those treated at the final ‘biologically selected dose’ (i.e. the tolerable dose associated with evidence of FGFR pathway pharmacodynamic modulation or of radiographic responses in FGFR biomarker selected cohorts) and the response rates in each biomarker selected cohort will be calculated within each cohort using only the number treated at this dose.

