Another role of the double negative cohort is to permit rapid patient accrual to assess the PD/dose determination markers early in the conduct of the study, being expanded as needed if doses less than 45mg QD have to be explored. In addition, it may generate 'atypical' *RET* and *FGFR1* negative responders, to be further explored in future.

The proportion of the initial 12 patients at 45mg QD (and in the 12 patients at any subsequent dose levels) demonstrating a $\geq 50\%$ increase in plasma FGF23 by Day15 (defined as a 'PD-response') will be assessed in the same statistical manner as radiographic responses in order to determine whether the dose/regimen used is affecting the FGFR pathway in normal tissues. A $\geq 50\%$ increase in plasma FGF23 measurements occurring in ≥ 3 of 12 patients will be considered indicative of FGFR inhibition (Shi et al, 2009). In addition, FGFR inhibition should be accompanied with a decrease in the fractional excretion of phosphorus in the urine (normal: 10-15%) and an elevation of serum phosphorus compared to baseline at the same time. If exposures are inadequate to affect these biomarkers (provided no evidence of tumor shrinkage has occurred in any of the FGFR+ cohorts by that point), higher doses/exposure regimens will not be explored. If 45mg is not-tolerated and insufficient patients treated to accurately assess efficacy, 30mg may be explored in the FGFR1 and double negative cohorts.

If doses other than 45mg QD have to be explored, the number of patients in each biomarker selected cohort will be modified to include only those treated at the final dose and the response rates in each biomarker selected cohort will be calculated within each cohort using only the number treated at this dose. The number of adverse events and percentages will be tabulated per organ and per visit. Kaplan-Meier survival curves will be used to display PFS and extra-CNS PFS (Camidge et

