FISH since June 2012, we have identified four positive cases to date (3 x KIF5B and 1 x CCDC6, based on cytogenic patterns). As our dataset expands, we will consider exploring other cutpoints in the future, and also defining equivocal or inconclusive cases suitable for additional interrogation e.g. by RT-PCR as a confirmatory assay.

3.4 Pharmacokinetics (PK):

No PK analyses for ponatinib will be conducted

in this study looking at either 30mg or 45mg QD. The exposures associated with a range of different doses of ponatinib have already been characterized within the initial phase I studies of this drug (Talpez et al, 2010). A once daily dose of 45mg of ponatinib taken orally has shown activity in patients with chronic myeloid leukemia and is taken to represent the recommended phase II dose of the drug. The geometric mean trough concentration at 45mg was 61.9nM and the mean steady state C_{max} was 149nM, suggesting that 45mg will achieve efficacious levels against FGFR1-4 in vivo (Talpez et al, 2010; Gozgit et al, 2012) (Figure 8).

However, if no evidence of pharmacodynamic effects in terms of either activity (tumor shrinkage) against FGF pathway selected patients or of clear modulation of host FGF-related metabolism (see section 3.2 above) is not seen within the initial patients treated at 45mg QD, because of the new data on long term risks associated with ponatinib higher doses/exposures will not be explored. If there is clear evidence of activity at 45mg, even if well tolerated, potentially lower doses (eg 30mg) may also be explored in the FGFR1 cohorts to mitigate safety in future studies. If 45mg is not tolerated per DLT criteria, 30mg will be explored in the FGFR1 cohorts, assuming insufficient patients were treated at 45mg to assess efficacy accurately. As the IC₅₀ for RET is an order of magnitude lower than for FGFR1, and the starting dose for the RET cohort will be 30mg, the logic relating to efficacious exposures for doses based on FGFR1 PD markers/responses will not automatically be applied to the RET+ cohort and if activity in RET+ cases is noted at the time this will not influence the decision-making re dose alteration in the FGFR1+ cohorts. However, if ≤ 2 responses are seen in the initial RET+ cohort but FGFR1+ responses or FGFR PD modulation have been noted at 45mg and 45mg appears acutely well tolerated per DLT criteria we will reconsider this logic and accrue an additional RET+ cohort at 45mg.

3.5 Pharmacogenomics (PG):

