2009). In addition, FGFR inhibition should be accompanied with a decrease in the fractional excretion of phosphorus in the urine (normal: 10-15%) and an elevation of serum phosphorus compared to baseline at the same time. If exposures are inadequate to affect these biomarkers (provided no evidence of tumor shrinkage has occurred in any of the FGFR+ cohorts by that point), due to the new data on risk factors associated with ponatinib, higher doses/dosing regimens of ponatinib will not be explored, however, if 45mg is not tolerable, but there is insufficient evidence to assess efficacy, 30mg will be considered for exploration in the FGFR-related cohorts. RET patients will commence at 30mg from the start due to the higher potency for ponatinib towards RET. A dose level will be considered tolerable following completion of 1 cycle (28 days) in 9 of 12 patients in the absence of dose limiting toxicity (DLT). If ≥ 3 patients experience DLT at this dose level, the dose level will be deemed non-tolerated.

If doses other than 45mg QD have to be explored, the number of patients in each biomarker selected cohort will be modified to include only those treated at the final 'biologically selected dose' (i.e. the dose associated with evidence of FGFR pathway PD modulation or of radiographic responses in FGFR+ cohorts) and the response rates in each biomarker selected cohort will be calculated within each cohort using only the number treated at this dose. The number of adverse events and percentages will be tabulated per organ and per visit. Kaplan-Meier survival curves will be used to display PFS and extra-CNS PFS (Camidge et al, 2011; Lin et al, 2012). Progression-free median time and 95% confidence interval will be reported. Proportions of failure due to CNS or extra-CNS will be reported along with 95% exact confidence intervals. Response duration will be summarized using median and range (min, max). Where biomarker overlap occurs, exploratory analyses of the differential effect of one biomarker over another will be explored across patients in all cohorts using multivariate analysis. Exploratory analyses will include assessing the impact of different SISH+ patterns, of higher cutpoints for FGFR1 SISH and ISH and the impact of FGF ligand levels on maximal percentage shrinkage per RECIST or PFS or duration of response in the FGFR1 SISH/ISH+ cohorts.

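### Exactly 3 DLTs among 12 evaluable patients makes a dose level both tolerable and non-tolerated, and nothing in the plan says which verdict governs

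*Combined protocol and SAP*

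**What the plan says.** Section 9.3 states the tolerability rule in two consecutive sentences. A dose level is "considered tolerable following completion of 1 cycle (28 days) in 9 of 12 patients in the absence of dose limiting toxicity (DLT"). Then: "If ≥ 3 patients experience DLT at this dose level, the dose level will be deemed non-tolerated". The same pair appears in the Study Synopsis, Section 1 (Objectives), Section 4.0 (Study Design) and Section 10.3 (Part B Analysis Plan).

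Section 9.3 also defines who counts. A patient without a DLT must take 24 of the 28 planned doses in cycle 1 to be evaluable. A non-evaluable patient "will be replaced if needed to determine adequate numbers for tolerability and dose decision making".

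The verdict feeds two dose decisions.

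- **30mg in the FGFR1 cohorts.** Section 3.4 says: "If 45mg is not tolerated per DLT criteria, 30mg will be explored in the FGFR1 cohorts, assuming insufficient patients were treated at 45mg". The Part B Analysis Plan in the Synopsis is softer: "If 45mg is not-tolerated and insufficient patients treated to accurately assess efficacy, 30mg may be explored in the FGFR1 and double negative cohorts". Section 10.3 says: "if 45mg is not tolerable, but there is insufficient evidence to assess efficacy, 30mg will be considered for exploration in the FGFR-related cohorts". Section 9.2 also opens 30mg from the other side: "if 45mg is tolerated and there is evidence (radiographic or pharmacodynamic) of efficacy, 30mg may be explored to establish a safer dose longterm".
- **A further RET+ cohort at 45mg.** Section 9.3 allows this after 2 or fewer RET+ responses, with FGFR1+ responses or pharmacodynamic modulation seen at 45mg, and if "45mg appears to be acutely well tolerated per DLT criteria we will reconsider this logic and accrue an additional" such cohort.

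**The concern.** A pre-specified safety rule should return one verdict for every outcome. Here the two sentences use thresholds that meet: 9 of 12 DLT-free is the same outcome as 3 of 12 with a DLT. The first sentence passes the dose and the second fails it.

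If that outcome occurs, the people reviewing the data must choose the verdict after seeing it. The plan itself describes fatal and life-threatening vascular occlusion with this drug and was amended to reduce that risk, so the tolerability call should not be left open. The verdict also reaches the efficacy analysis by one route. In the Synopsis and Sections 1, 4.0 and 9.3 the biologically selected dose must be a tolerable one, and if doses other than 45mg are explored, only patients at that dose count in the response rates. Section 10.3 gives the same definition without the word tolerable.

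**Working it through.** **Inputs.** From Section 9.3: tolerable if 9 of 12 are DLT-free (read as at least 9); non-tolerated if 3 or more have a DLT; an evaluable patient either has a DLT or meets the dosing minimum without one. The last input is taken to mean that each DLT-free evaluable patient counts as having completed cycle 1. The plan states no DLT rate and no operating characteristics for this rule, so there is no figure of its own to reproduce.

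**Step 1: enumerate the outcomes.** With 12 evaluable patients and d DLTs, 12 − d are DLT-free. Tolerable requires 12 − d ≥ 9, that is d ≤ 3. Non-tolerated requires d ≥ 3.

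| DLTs (d) | DLT-free | First sentence | Second sentence |
|---|---|---|---|
| 0 to 2 | 12 to 10 | tolerable | not triggered |
| 3 | 9 | tolerable | non-tolerated |
| 4 to 12 | 8 to 0 | not met | non-tolerated |

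Of 13 possible outcomes, d = 3 is the only overlap. Reading the first sentence as exactly 9 leaves the conflict at d = 3 unchanged.

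**Step 2: allow for unreplaced non-evaluable patients.** With m of the 12 non-evaluable and unreplaced, tolerable requires 12 − m − d ≥ 9, so d ≤ 3 − m. Together with d ≥ 3 this forces m = 0. For example, 9 DLT-free, 2 DLTs and 1 unreplaced patient is tolerable under both sentences.

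**Step 3: size.** Let X be the number of DLTs, Binomial(12, p), with p assumed:

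P(X = 3) = C(12,3) p³ (1 − p)⁹ = 220 p³ (1 − p)⁹.

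At p = 0.20: 220 × 0.008 × 0.1342 = 0.2362.

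If the second sentence governs, P(non-tolerated) = P(X ≥ 3). If the first governs, it is P(X ≥ 4). The difference is P(X = 3).

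| True DLT rate | P(X = 3) | P(X ≥ 3) | P(X ≥ 4) |
|---|---|---|---|
| 5% | 0.0173 | 0.0196 | 0.0022 |
| 10% | 0.0852 | 0.1109 | 0.0256 |
| 15% | 0.1720 | 0.2642 | 0.0922 |
| 20% | 0.2362 | 0.4417 | 0.2054 |
| 25% | 0.2581 | 0.6093 | 0.3512 |
| 30% | 0.2397 | 0.7472 | 0.5075 |
| 40% | 0.1419 | 0.9166 | 0.7747 |

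P(X = 3) peaks at p = 3/12 = 0.25, at 0.2581.

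**Step 4: look for a tie-break.** Section 9.3 covers evaluability and replacement. Section 11.6 has toxicity reviewed after each of the first 12 patients and refers to stopping rules and institutional policy. Section 11.9 lets the monitoring committee suspend or close the trial. None of them ranks the two sentences.

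**The case against.** The best defence is that the second sentence plainly overrides. It comes later, is the more cautious of the two, is phrased as mandatory, and the dose decisions refer back to the DLT criteria. On this view the 9 of 12 is a completion floor that leaves room for a non-evaluable patient, and the 3-DLT limit is a cap. This is a sensible default, and the first fix below adopts it. But the plan does not state it, and with 12 evaluable patients it would mean that 9 DLT-free never suffices and 10 are needed. Another reader could as fairly hold that 9 of 12 was the intended threshold.

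A second argument uses the running review in Section 11.6. If the verdict were fixed as soon as a third DLT occurred, the sentences would collide only when that DLT was the last of the 12 outcomes. With exchangeable order that is 3/12 of the cases: 0.25 × 0.0852 = 2.1%, 0.25 × 0.2362 = 5.9% and 0.25 × 0.2581 = 6.5% at rates of 10%, 20% and 25%. The arithmetic is right, but the plan does not say the verdict is fixed at that moment. What stands is that the larger figures assume a count at the end of 12 evaluable patients.

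Third, the reach is limited. The verdict alone settles neither dose decision. 30mg after a non-tolerated verdict also needs insufficient efficacy data at 45mg, and with radiographic or pharmacodynamic evidence 30mg can follow a tolerated verdict too. Section 9.2 rules out doses above 45mg. All of this stands.

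**Conclusion.** The concern holds. With 12 evaluable patients the rule contradicts itself at exactly 3 DLTs and nowhere else, in all five places where it appears, and no section says which sentence prevails. The chance of reaching that outcome is 2% to 26% for assumed true DLT rates of 5% to 40%. The 26% is a maximum, not an expected value. The figures rest on independent patients with a common DLT rate and on a verdict taken when all 12 are evaluable.

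This is a small inconsistency in a safety rule and should be corrected. For the 30mg decision it matters mainly when there is no evidence of efficacy at 45mg, because with such evidence 30mg can follow either verdict. For the extra RET+ cohort it matters only if the other conditions are met. The threshold of 3 responses in 12 for the primary endpoint is not affected, although the verdict can bear on which dose group is counted if doses other than 45mg are explored.

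**What to change.** Let the DLT limit govern. In the Synopsis and Sections 1, 4.0, 9.3 and 10.3, add to the tolerable sentence: *and fewer than 3 patients experience DLT*. Writing *at least 9* in the same sentence would remove any doubt about that threshold. With 12 evaluable patients the rule then requires at least 10 of 12 DLT-free. The case of 9 DLT-free, 2 DLTs and 1 unreplaced patient stays tolerable, so the replacement rule needs no change.

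The price is a stricter verdict than the other resolution. P(non-tolerated) at true DLT rates of 10%, 15%, 20% and 25% is 0.11, 0.26, 0.44 and 0.61, against 0.03, 0.09, 0.21 and 0.35 with a trigger of 4 or more DLTs. If the clinical team regards 3 of 12 as acceptable, keep 9 of 12 and raise the trigger to 4 or more.

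Either way the change is a short wording edit in five places. Sample size, visits and data collection are unchanged.

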Nonhematologic Toxicity	
General	
Grade 1 or transient Grade 2	No intervention
Grade 2 lasting ≥ 7 days with optimal care	
Hold ponatinib Resume at 45 mg after recovery to \leq grade 1
 
Recurrence at 45 mg: Hold ponatinib Resume at 30 mg after recovery to \leq grade 1
 
Recurrence (or Occurrence if 30mg starting dose) at 30 mg Hold ponatinib Resume at 15 mg after recovery to \leq grade 1
 
Recurrence at 15 mg Consider discontinuing ponatinib

Grade 3 or 4	
Hold ponatinib Resume at 30 mg after recovery to \leq grade 1
 
Recurrence (or Occurrence if 30mg starting dose) at 30 mg Hold ponatinib Resume at 15 mg after recovery to \leq grade 1
 
Recurrence at 15 mg Consider discontinuing ponatinib

Pancreatitis	
Grade 2 (enzyme elevation or radiologic findings only)	See amylase/lipase section below
Grade 3 (severe pain, vomiting, medical intervention indicated [eg, analgesia, nutritional support])	
Hold ponatinib Perform ultrasound or abdominal CT scan with contrast If imaging is positive, continue holding ponatinib and repeat according to clinical care If imaging is negative, or after resolution by imaging, resume at 30 mg after recovery to \leq grade 1
 
Recurrence (or Occurrence if 30mg starting dose) at 30 mg: Repeat above, except resume at 15 mg after recovery to \leq grade 1
 
Recurrence at 15 mg: Repeat above Consider discontinuing ponatinib

Toxicity	Modification
Grade 4	Discontinue ponatinib
Amylase/Lipase	
Grade \leq 2	No intervention; monitor closely
Grade 3 with no radiologic findings	
Hold ponatinib Resume at 45 mg after recovery to \leq grade 1
 
Recurrence at 45 mg: Hold ponatinib Resume at 30 mg after recovery to \leq grade 1
 
Recurrence (or Occurrence if 30mg starting dose) at 30 mg: Hold ponatinib Resume at 15 mg after recovery to \leq grade 1
 
Recurrence at 15 mg: Hold ponatinib Consider discontinuing ponatinib

Grade 3 with radiologic findings or Grade 4	
Hold ponatinib Repeat imaging according to clinical care After resolution by imaging, resume at 30 mg after recovery to \leq grade 1
 
Recurrence (or Occurrence if 30mg starting dose) at 30 mg: Repeat above Resume at 15 mg after recovery to \leq grade 1
 
Recurrence at 15 mg: Repeat above Consider discontinuing ponatinib

LV dysfunction/CHF	

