11.0 ADVERSE EVENT REPORTING AND STUDY CONDUCT

11.1 Definitions

11.1.1 Adverse Event (AE)

An adverse event (AE) is any undesirable sign, symptom or medical condition or experience that develops or worsens in severity after starting the first dose of study treatment or after any procedure specified in the protocol, even if the event is not considered to be related to the study.

Abnormal laboratory values or diagnostic test results constitute adverse events only if they induce clinical signs or symptoms or require treatment or further diagnostic tests.

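### Section 9.3 lets a patient held 5 to 14 days for drug toxicity be neither a DLT nor evaluable, and be replaced, although tolerability is judged by completion of the cycle in 9 of 12

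*Combined protocol and SAP*

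**What the plan says.** The tolerability rule in Section 9.3 has two limbs. The first reads "A dose level will be considered tolerable following completion of 1 cycle (28 days) in 9 of 12 patients in the absence of" DLT. The second declares the dose level non-tolerated at three or more DLTs. Section 10.3 repeats both limbs without any evaluability or replacement rule.

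The DLT list in 9.3 includes "Any treatment delay of > 14 days due to drug-related toxicity". The evaluability rule is "Patients must complete 24 of the planned 28 days (85%) dosing of ponatinib in Cycle 1 to be evaluable in the absence of DLTs". For a patient who falls short, the text continues: "If not evaluable for the purposes of determination of drug tolerability, the patient may continue to be treated, but will be replaced if needed". No distinction is made by the reason for the missed doses.

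Section 9.4 orders holds for toxicities that are not on the DLT list. Examples are a grade 2 non-hematologic event "lasting ≥ 7 days with optimal care", persistent grade 2 rash, grade 3 neutrophil or platelet toxicity, and grade 2 transaminase elevation. Dosing resumes only after recovery to grade 1 or less. The same section says that days lost to a hold are not made up later.

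**The concern.** A tolerability set should not lose patients because they did not tolerate the drug. Here the protocol's own hold rules can push a patient below 24 doses for drug toxicity, and the evaluability rule then lets that patient leave the 12. The first limb of the verdict treats failure to complete the cycle as evidence against the dose. The replacement rule treats the same failure as missing information. The two pull in different directions.

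The verdict feeds two later steps. One is exploring 30mg in the FGFR1 cohorts, which also requires that too few patients were treated at 45mg to assess efficacy. The other is opening an additional RET cohort at 45mg, which also requires 2 or fewer RET responses plus FGFR1 responses or pharmacodynamic modulation.

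**Working it through.** **Evaluability threshold.** 24/28 = 85.7%, which the protocol prints as 85%. In the other direction, 0.85 × 28 = 23.8, rounded up to 24. The smallest number of missed days that makes a patient without a DLT non-evaluable is 28 − 24 + 1 = 5.

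**Classification of one continuous toxicity hold that is not a DLT by another route.**

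| Missed days in Cycle 1 | DLT? | Evaluable? | Status |
|---|---|---|---|
| 0–4 | no | yes | counts as no DLT |
| 5–14 | no | no | may be replaced |
| 15 or more | yes | yes | counts as DLT |

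The 5–14 day window follows directly from the two thresholds. The text does not say whether separate holds are added together or how a hold running into Cycle 2 is treated, so the table is for a single hold.

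**Limit of the gap.** Grade 3 or higher non-hematological events (apart from the stated gastrointestinal exclusion), grade 4 thrombocytopenia and qualifying grade 4 neutropenia are DLTs however many days are missed. Only lesser toxicities fall into the window.

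**Size.** The documents state neither a DLT rate p nor a rate q of 5–14 day toxicity holds without a DLT. Both are assumed below, with patients independent.

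- *As written, always replaced.* Patients are added until 12 are evaluable. The DLT rate among evaluable patients is r = p/(1 − q). All evaluable patients without a DLT have taken at least 24 doses, so the three-DLT limb decides: P(tolerable) = P(X ≤ 2), X ~ Binomial(12, r).
- *Retained as non-completers, both existing rules kept.* With x DLTs and y gap patients among a fixed 12, tolerable requires x ≤ 2 and x + y ≤ 3. P = Σ 12!/(x! y! (12−x−y)!) · p^x q^y (1−p−q)^(12−x−y) over those pairs.
- *Retained as evaluable without a DLT.* P = P(X ≤ 2), X ~ Binomial(12, p).

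Exactly 3 DLTs with 9 completers would satisfy both limbs of the protocol rule. It is treated here as non-tolerated throughout.

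Worked example, p = q = 0.15. As written, r = 0.15/0.85 = 0.176, and the terms for 0, 1 and 2 DLTs are 0.097 + 0.250 + 0.295 = 0.64. Retained as non-completers, the terms for x = 0, 1 and 2 are 0.121 + 0.209 + 0.132 = 0.46. Retained as evaluable without a DLT, the result is 0.74.

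| p / q (assumed) | r | As written | Non-completers | Evaluable, no DLT |
|---|---|---|---|---|
| 10% / 5% | 0.105 | 0.88 | 0.86 | 0.89 |
| 10% / 10% | 0.111 | 0.86 | 0.77 | 0.89 |
| 15% / 15% | 0.176 | 0.64 | 0.46 | 0.74 |
| 10% / 20% | 0.125 | 0.82 | 0.48 | 0.89 |

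The expected number treated to reach 12 evaluable patients is 12/(1 − q): 12.6, 13.3, 14.1 and 15.0 for the four rows.

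**The case against.** A reader might infer that the verdict is biased toward tolerable whatever the comparison. The documents do not support that. The DLT list, taken alone, makes these patients non-DLTs. If they stayed in the 12 on that footing, a tolerable verdict would be more likely than as written (last column), because replacement removes non-DLT patients and raises the evaluable DLT rate to p/(1 − q). For the same reason it is wrong to suppose that each replacement is someone who tolerated the drug; a replacement can have a DLT and would count. The direction claimed here holds only against the completion criterion.

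The two parts of 9.3 can also be read together: 24 of 28 days defines completion, and the 12 are formed from patients who meet it or have a DLT. That reading is coherent, but it leaves the completion limb almost nothing to do, since non-completers without a DLT never enter the count. Replacement is also only if needed, not automatic.

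These patients are not hidden. Section 10.4 keeps every treated patient in toxicity reporting, and Sections 11.6, 11.7 and 11.9 provide for toxicity review, stopping for excessive toxicity, and reporting of dose modifications. This limits the harm but does not return them to the 12-patient verdict. The 11.6 review is triggered by completing Cycle 1 or having a DLT, and on the 24-day reading of completion they do neither.

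A reader might add that laboratory DLTs escape through Section 11.1.1, which says "Abnormal laboratory values or diagnostic test results constitute adverse events only if they induce clinical signs or symptoms". The sentence goes on to include abnormalities needing treatment or further tests. The listed laboratory DLTs would ordinarily need repeat testing, so that point is not made.

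**Conclusion.** The gap is exact on the text: one drug-toxicity hold of 5 to 14 days, with no other DLT, leaves a patient neither a DLT nor evaluable, and replaceable. Because the reason for leaving is toxicity, the replacement is informative. Measured against the protocol's own 9-of-12 completion criterion, it favours a tolerable verdict.

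The size depends on the assumed rates. With both existing rules kept, the probability of a tolerable verdict differs by about 0.02 when gaps are rare (10%/5%), by about 0.09 at 10%/10%, by 0.18 at 15%/15%, and by about a third at 10%/20%. A large effect should not be inferred without evidence that such holds are common, and the documents give none. A reader might also carry these figures straight over to the 30mg and RET decisions. The protocol ties those to tolerability per DLT criteria and to further conditions, so the figures do not transfer.

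**What to change.** In Section 9.3, limit replacement to patients who miss Cycle 1 doses for reasons unrelated to the drug. Keep toxicity-related non-completers in the 12-patient tolerability set, and report their number and the reasons for the missed doses alongside the verdict. Carry the same wording into Section 10.3.

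The sponsor must reconcile the two limbs of the tolerability rule (9 of 12 completing; three or more DLTs) with the 24-of-28-day evaluability rule, and state before data are reviewed how the retained patients count. No DLT definition, hold rule or dose is proposed here.

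The cost is a protocol wording change. The tolerability result may look slightly less favourable, depending on how the sponsor decides these patients count and how many there are. Fewer replacement patients would be needed.
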